Final Protocol:	June 2019	Clean File:	June 2019
Ethics Approval:	January 2019	Statistical analysis:	
Clinical Phase:		Study Report:	
OBJECTIVES:	To compare the safety and efficacy of administering intravenous autologous cord blood versus personalized noninvasive treatments to children with developmental disorders of the autistic spectrum		
STUDY DESIGN:	An open-label, pilot crossover study over a 12-month period. Participants will be screened and randomized at Visit 0 and at visit V1 will be receiving either intravenous umbilical cord blood or noninvasive treatment. At V2, at 2 months after V1, the other treatment is administered and subsequently the child will be evaluated by questionnaires and child therapist. Parents will report adverse events and complete the M-CHAT, Q-CHAT and CAST questionnaires. Modifications on these questionnaires will be analyzed statistically as a quantitative measure of child's improvement.		
SUBJECTS:	
Inclusion criteria Males and females between 3 and 7 years of age:
 
 • parents informed of the nature of the study and will give written informed consent, • have body weights between 10-30 kg, • have no clinically significant abnormal values on hemoleucogram during screening, • be on no regular medical treatment • have no known allergies to treatments 
Exclusion criteria
 
 • Any genetic or metabolic disease or condition which might compromise the haematopoietic, renal, endocrine, pulmonary, central nervous, cardiovascular, immunological, dermatological, gastrointestinal or any other body system. • History of allergic conditions – asthma, urticaria, eczema. • History of autoimmune disorders 		

	
 • Intake of any medication within 14 days before start of the study • Presence of significant abnormal hemoleucogram results during screening.
TREATMENT TO BE EVALUATED	
Active Treatment A: Autologous umbilical cord blood administered intravenously as single treatment .
 
Active Treatment B: Personalized daily treatment following evaluation with a combination of intranasal Oxytocin; Curcumin; Lecithin, Piracetam, Tecfidera; PQQ; Magnesium citrate and vitamin B6

DURATION OF STUDY	12 months
ENDPOINTS:	
EFFICACY
 
 1. Behavioral improvement with the validated scales for autistic spectrum disorders 2. Examination by child psychologist 
SAFETY
 
 1. Adverse events, especially frequency and intensity of agitation episodes 2. Modification of vital signs: blood pressure, heart rate, respiratory rate, body temperature. 3. Modification of laboratory tests: Haematology: RBC, MCHC, MCH, MCV, RDW, Hct, Hb, WBC Differential count –lymphocytes monocytes, neutrophils, eosinophils, basophils; CD45+; blood cultures Biochemistry: Serum - Bilirubin (total) AST, ALT, LDH, glucose, urea, creatinine, sodium, potassium, chloride, calcium., MB microbiology; IP – Inflammatory panel
SAMPLE SIZE:	at least 25 patients, optimum 40 patients enrolled
STATISTICAL ANALYSIS:	Summary statistics will describe the safety variables. Significance testing will be done using analysis of variance for continuous and chi-square test for categorical variables. ($\alpha = 0,05$)

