1. INTRODUCTION

1.1 Abstract

1. The treatment of children with autistic spectrum disease (ASD) represents a serious challenge for both the patients and their families, and also the medical staff involved.

Recently (Dawson G, 2017) prof Geraldine Dawson from Duke University showed that the use of stem cells from autologous umbilical cord blood (UCB) is a safe and efficacious therapy, opening a new and exciting avenue for therapeutic redress in children with ASD. This new therapeutic venue has yielded more dramatic improvements than any previous treatment including intranasal oxytocin.

We know that ASD has multiple determinants - genetic, environmental, neurological, and immunological (Young 2016) – and the pathological processes involved in ASD are various and complex. ASD is after all a spectrum of diseases involving brain development, not just a well-defined condition, and the implication is that the one-molecule-fits-all type of treatment will not be likely to address the multitude of aspects and deficiencies which are present in individuals with ASD. UCB itself contains a plethora of molecules which can modulate the activities of neurons and the supporting microglia, so comparing it with just one therapeutic substance would not be a good strategy.

With this in mind, we propose that ASD treatment should be very much personalized after a careful evaluation of the patient, and a noninvasive treatment option should include two or more substances from the following: oxytocin, curcumin, magnesium citrate with vitamin B6, pironoquinolinquinone (PQQ), lecithin, piracetam, and optionally dimethylfumarate, a medication known to be both neuroprotective and immunomodulatory.

Below we propose a pilot clinical study which aims to compare the safety and efficacy of UCB administration versus a less invasive and costly therapeutic option which consists of a patient-specific combination of medications and supplements. The study will be open-label, crossover type, meaning that all children will get sequentially both treatments after a 2-week washout interval. This study design has the advantage of eliminating the ethically questionable administration of a placebo.

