4 STUDY MEASUREMENTS AND ENDPOINTS

In this study the following endpoints will be measured/recorded

1. Efficacy - difference in the scores on the questionnaires M-CHAT, Q-CHAT and CAST before and after each treatment

2. Safety – type, severity, duration, treatment and amelioration of each of the adverse effects occurring during respective treatments.

4.1 Primary Safety Endpoints.

–

1. Adverse events (type and frequency)
2. Physical examination parameters (body mass, height, etc)
3. Vital signs: blood pressure, heart rate, respiratory rate, body temperature
4. Laboratory tests
 - HLA testing by genetic sequencing
 - Haematology: CBC - RBC, HB, MCHC, MCH, MCV, RDW, Hct, Hb, WBC Differential count –lymphocytes monocytes, neutrophils, eosinophils, basophils, flowcytometry - CD34+, TNC, viability %
 - Microbiology – presence and sensitivity of pathogens
 - LFTs Serum - Bilirubin (total and conjugated) AST, ALT, GGT, LDH, glucose
 - IP – serum protein electrophoresis, ESR, CRP, fibrinogen
 - Els - sodium, potassium, chloride, calcium, magnesium.

4.2 Measurements at each visit.

See section 3.1.1 for the visit schedule.

Visit 0: Screening Visit

Patients will be examined within 14 days prior to the first ingestion of the investigational products to assess their eligibility to participate. For each child both parents will consent in writing (Appendix 1, Informed Consent Form) to the screening process before the start of the examination. The consent form will also include the study information leaflet.

The examinations and investigations will include:

- Medical history, including history of past use of medications, demographics (date of birth, sex, race) and ASD diagnosis.
- Physical examination including assessment of general appearance, cardiovascular, lungs, mouth, throat and abdomen and measurement of height and body weight. The examination will be made in accordance with the normal clinical routines at the trial center.
- Vital signs: systolic and diastolic blood pressure in supine (after 5 minutes rest) and standing positions (1minute), pulse, respiratory rate and oral temperature.
- Laboratory tests: HLA, Haematology, (see section 4.4.3.2); baseline plasma levels of IP, Els, LFTs (these can be drawn also at V1 if considered by the study PI)

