5 STATISTICAL METHODS

5.1 Determination of sample size

Based on literature we expect that a sample size of minimum 25 participants will be needed in order to observe an alpha value of 0.05 (95% probability) with a p value of 0.05 and a power of 80%. ANOVA testing will be performed on the respective groups of patients

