12. Can s/he read appropriately for his/her age? Yes No
13. Does s/he mostly have the same interests as his/her peers? Yes No
14. Does s/he have an interest which takes up so much time that s/he does little else? Yes No
15. Does s/he have friends, rather than just acquaintances? Yes No
16. Does s/he often bring you things s/he is interested in to show you? Yes No
17. Does s/he enjoy joking around? Yes No
18. Does s/he have difficulty understanding the rules for polite behaviour? Yes No
19. Does s/he appear to have an unusual memory for details? Yes No

- 20. Is his/her voice unusual (e.g., overly adult, flat, or very monotonous)? Yes No
- 21. Are people important to him/her? Yes No
- 22. Can s/he dress him/herself? Yes No
- 23. Is s/he good at turn-taking in conversation? Yes No
- 24. Does s/he play imaginatively with other children, and engage in role-play? Yes No
- 25. Does s/he often do or say things that are tactless or socially inappropriate? Yes No
- 26. Can s/he count to 50 without leaving out any numbers? Yes No
- 27. Does s/he make normal eye-contact? Yes No
- 28. Does s/he have any unusual and repetitive movements? Yes No
- 29. Is his/her social behaviour very one-sided and always on his/her own terms? Yes No
- 30. Does s/he sometimes say “you” or “s/he” when s/he means “I”? Yes No
- 31. Does s/he prefer imaginative activities such as play-acting or story-telling, rather than numbers or lists of facts?
Yes No
- 32. Does s/he sometimes lose the listener because of not explaining what s/he is talking about? Yes No
- 33. Can s/he ride a bicycle (even if with stabilisers)? Yes No
- 34. Does s/he try to impose routines on him/herself, or on others, in such a way that it causes problems? Yes No
- 35. Does s/he care how s/he is perceived by the rest of the group? Yes No
- 36. Does s/he often turn conversations to his/her favourite subject rather than following what the other person wants to talk about? Yes No
- 37. Does s/he have odd or unusual phrases? Yes No

SPECIAL NEEDS SECTION

Please complete as appropriate

- 38. Have teachers/health visitors ever expressed any concerns about his/her development? Yes No

If Yes, please specify.....

- 39. Has s/he ever been diagnosed with any of the following?:

- Language delay Yes No
- Hyperactivity/Attention Deficit Disorder (ADHD) Yes No
- Hearing or visual difficulties Yes No
- Autism Spectrum Condition, incl. Asperger’s Syndrome Yes No
- A physical disability Yes No
- Other (please specify) Yes No

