1. Does your child look at you when you call his/her name?
 - always
 - usually
 - sometimes
 - rarely
 - never
2. How easy is it for you to get eye contact with your child?
 - very easy
 - quite easy
 - quite difficult
 - very difficult
 - impossible
3. When your child is playing alone, does s/he line objects up?
 - always
 - usually
 - sometimes
 - rarely
 - never
4. Can other people easily understand your child's speech?
 - always
 - usually
 - sometimes
 - rarely
 - never
 - my child does not speak
5. Does your child point to indicate that s/he wants something (e.g. a toy that is out of reach)?
 - many times a day
 - a few times a day
 - a few times a week
 - less than once a week
 - never

Please answer the following questions about your child by ticking the appropriate circle.
Try to answer EVERY question if you can.

6. Does your child point to share interest with you (e.g. pointing at an interesting sight)?
 - many times a day
 - a few times a day
 - a few times a week
 - less than once a week
 - never
7. How long can your child's interest be maintained by a spinning object (e.g. washing machine, electric fan, toy car wheels)?
 - several hours
 - half an hour
 - ten minutes
 - a couple of minutes

- less than a minute
8. How many words can your child say?
- none—s/he has not started speaking yet
 - less than 10 words
 - 10–50 words
 - 51–100 words
 - over 100 words
9. Does your child pretend (e.g. care for dolls, talk on a toy phone)?
- many times a day
 - a few times a day
 - a few times a week
 - less than once a week
 - never
10. Does your child follow where you're looking?
- many times a day
 - a few times a day
 - a few times a week
 - less than once a week
 - never
11. How often does your child sniff or lick unusual objects?
- many times a day
 - a few times a day
 - a few times a week
 - less than once a week
 - never
12. Does your child place your hand on an object when s/he wants you to use it (e.g. on a door handle when s/he wants you to open the door, on a toy when s/he wants you to activate it)?
- many times a day
 - a few times a day
 - a few times a week
 - less than once a week
 - never
13. Does your child walk on tiptoe?
- always
 - usually
 - sometimes
 - rarely
 - never
14. How easy is it for your child to adapt when his/her routine changes or when things are out of their usual place?
- very easy
 - quite easy
 - quite difficult
 - very difficult
 - impossible

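### Efficacy is written as before-after change on each treatment, with no untreated comparison and no written A-versus-B contrast, so ordinary score drift could be reported as improvement

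*Combined protocol and SAP*

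**What the plan says.** The synopsis (Study design) says of the M-CHAT, Q-CHAT and CAST: "Modifications on these questionnaires will be analyzed statistically as a quantitative measure of" the child's improvement. Section 4 defines the efficacy endpoint as "difference in the scores on the questionnaires M-CHAT, Q-CHAT and CAST before and after each treatment".

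Both treatments are active. Section 1.1 presents this as a strength: "This study design has the advantage of eliminating the ethically questionable administration of a placebo". No untreated group, waiting list, age norm or age adjustment is described.

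The objective is comparative: the synopsis and Section 2 both speak of comparing the two treatments, and Section 3.1 randomises their order. On method, the synopsis names analysis of variance and chi-square, and Section 5.1 adds only that ANOVA will be done on the respective groups of patients. Section 5.2 covers baseline description and safety and contains no efficacy analysis.

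Section 3.1.1 schedules the questionnaires at V0, V2 (8 weeks after V1), V3 (16 weeks), V4 (24 weeks) and V5 (52 weeks). The second treatment starts at V2.

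**The concern.** A before-after change on one treatment mixes any effect of that treatment with everything else that moves the score. Three such influences are present here:

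- **Development.** The children are young and are followed for a year. Some questionnaire items ask about skills that children acquire with age, for example "Can s/he count to 50 without leaving out any numbers" (Annex 2, CAST) and "How many words can your child say" (Annex 4, Q-CHAT).
- **Regression to the mean**, if children enter when their scores are poor.
- **Expectation.** Parents complete the questionnaires and know which treatment was given.

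None of these needs a working treatment, and without an untreated comparison none can be separated from a treatment effect within one arm. The first question in the Study Rationale is what can be recommended to children without stored cord blood, and with what comparative efficacy. A significant before-after change on treatment B could be taken as an answer, although it would not be one.

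**Working it through.** **1. The plan's own figure.** Section 5.1 states: "Based on literature we expect that a sample size of minimum 25 participants will be needed", "with a p value of 0.05 and a power of 80" per cent. It gives no effect size, SD or within-child correlation, so 25 cannot be reproduced. Solving backwards for a paired comparison (two-sided 5%, 80% power): (1.960 + 0.842)/√25 = 0.56 SD, or 0.58 SD with the t distribution. Read as two groups of 12 and 13, the detectable difference is 1.17 SD. The figure does not show which comparison was meant.

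**2. Within-treatment test under drift alone.** Inputs: n = 25 (Section 5.1); alpha 0.05 (Sections 5.1 and synopsis), taken as two-sided; true treatment effect zero; drift m in SD units of the change, **assumed**. The paired t-test has 24 df, critical value 2.064 and noncentrality m√n. The chance of a significant change in the direction of improvement is P(t₂₄(m√25) > 2.064). The n = 40 column is the synopsis optimum (39 df, critical value 2.023).

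| Assumed drift m | m√25 | n = 25 | n = 40 |
|---|---|---|---|
| 0 | 0 | 2.5% | 2.5% |
| 0.1 | 0.5 | 7% | 9% |
| 0.2 | 1.0 | 16% | 23% |
| 0.3 | 1.5 | 30% | 46% |
| 0.4 | 2.0 | 48% | 69% |
| 0.5 | 2.5 | 67% | 87% |

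More children make the misleading result more likely.

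**3. The randomised contrast under the same drift.** A 2×2 crossover was simulated with no treatment effect and independent changes of SD 1. With 13/12 sequences and drift of 0.3 or 0.5 in both periods, the A-minus-B test rejects in about 5% of trials and the mean difference is 0.

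**4. When the contrast needs a period term.** If drift is m₁ in the first period and m₂ in the second, the unadjusted mean A-minus-B difference is (n_AB − n_BA)/n × (m₁ − m₂). With 17/8 sequences the first factor is 9/25 = 0.36.

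| m₁, m₂ | Bias | Type I error, no period term | With period term |
|---|---|---|---|
| 0.5, 0.2 | 0.36 × 0.3 = 0.108 | about 6% | 5% |
| 0.8, 0.2 | 0.36 × 0.6 = 0.216 | about 9% | 5% |

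Unequal drift is plausible from the schedule itself. If the first interval is scored from V0 to V2, it includes the gap before V1. That gap is 7 to 14 days in Section 3.1.1, making 9 to 10 weeks, and 14 to 21 days in Section 3.3.1, making 10 to 11 weeks. The second interval, V2 to V3, is 8 weeks. The allocation ratio is not stated, so balance cannot be assumed.

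**5. Later visits.** From V2 on, every child who continues has started both treatments. A change from V0 to V3, V4 or V5 pooled over all children therefore belongs to neither treatment alone.

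**The case against.** The strongest reply is that the trial is comparative throughout. The objective is comparative, the order is randomised, and a change score for each treatment is an ordinary outcome variable for comparing A with B. To say that the score measures improvement is not to say that the treatment caused it. No section specifies a within-arm test, and an active comparator without placebo is an open choice in a pilot. The rationale's question about children without cord blood also asks for comparative efficacy.

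Much of this stands. A reader might infer that normal development *will* be reported as a treatment effect in both arms. The documents do not support that: they plan no such test and announce no such claim. Nor do the percentages above describe both arms together. If the two changes were independent, both would be significant in 0.302² = 9%, 0.484² = 23% or 0.670² = 45% of trials. A reader might also read a week-52 change as a within-arm result, but it belongs to neither arm.

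The item evidence has limits as well. The annexes reproduce the questions without a scoring key, so the documents do not show that each age-related item enters a total. Some items ask about the past and should not change. How far the totals drift over 8 weeks cannot be learned from the documents.

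What the reply does not supply is an efficacy analysis. The comparative intent stands in the objectives; the endpoint is written as before-after change, and nothing connects the two. Section 4.2 has the questionnaires handed to parents at V1, while the schedule table names none there. Even if they were scored at V1, an untreated interval of one to three weeks is not used anywhere as a comparison.

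**Conclusion.** The point holds as a gap in the written endpoint and analysis. Applied literally, the Section 4 endpoint lets drift, regression to the mean and unblinded parent rating count as improvement, and no text restricts the efficacy claim to the randomised contrast. The 30%, 48% and 67% figures illustrate one paired test with 25 children, no treatment effect and assumed drift of 0.3, 0.4 or 0.5 SD; they do not predict what this trial will report. The near-5% figure for A-minus-B requires balanced sequences and equal drift in both periods, or a period term.

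The design can support a statement about relative efficacy only. If A and B do not differ, the trial cannot tell whether both work or neither does. Carry-over from the first treatment is a separate question that this point does not settle.

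**What to change.** In the synopsis and Section 4, and as a new efficacy paragraph in Section 5.2, state that:

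1. The efficacy result is the A-minus-B difference in questionnaire change over the two treatment periods (V0 to V2 and V2 to V3), from a crossover model with treatment, period and sequence terms. Say whether V0 or V1 is the first baseline, and reconcile the V0-to-V1 interval between Sections 3.1.1 and 3.3.1.
2. Changes within A, within B, and pooled over all children from V0 to V3, V4 or V5 are described without p-values and are not evidence that either treatment works. Randomised comparisons between the two sequences remain allowed at any visit.
3. A null A-minus-B result cannot separate the case where both treatments work from the case where neither does.

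The cost is a few sentences, with no added child, visit or test. The trial gives up within-arm significance claims, which its design cannot support. If the sponsor wants to claim that either treatment works in absolute terms, wording will not be enough: that needs an untreated comparison.

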3. ***Lecithin 500 mg bid*** will be administered if brain imaging reveals any demyelination/myelination deficits, global cerebral atrophy or regional atrophy

4. ***Magnesium citrate with vitamin B6 (150 mg/6 mg qd)*** will be included if restlessness/agitation/anxiety is present significantly in the clinical picture

5. ***Piranoquinolinquinone (PQQ) 20 mg/day*** will be administered in situations of apathic/disinterested behavior, marked introversion, marked developmental delays

6. ***Optional medication for special situations***, with parent's clear understanding, a few other treatment options will be included – ex.

- Tecfidera (dimethyl fumarate) 60 mg bid with food (presence of hypo/demyelination with an autoimmune component); immune modulation is involved in ASD as documented in Kornberg, 2018
- Boswellia extract 400 mg bid – decreases activation of NfK-beta which is the main modulator of both inflammation and neuronal connections
- piracetam (Nootropil) 400 mg bid (presence of severe developmental delays with low motor coordination and energy levels)
- Bacopa monieri (presence of demyelination in absence of immune over-activation)
- Uridine (inflammation mitigation, mitochondrial function stimulation)
- Hipophae rhamnoides oil (source of omega-7 unsaturated fatty acids for synaptic vesicles)

The decision of which of these components should be given is taken after all tests are done and the child psychologist/therapist and the study investigator discuss the case and afterwards discuss the practical issues of administering the recommended treatment with the parents.

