4.3 Specific detail on measurements

4.4.1 Adverse events

An adverse event is the development of an undesirable medical condition - e.g. symptoms or abnormal results of an investigation - or the deterioration of a pre-existing medical condition (not relevant in this study). AE's will be collected by means of a standard question: "Have you had any health problems since the previous visit?" AE's will be recorded at every visit. Spontaneously reported AE's and/or observed AE's and the subject's response to this question will be recorded on the AE form with information about seriousness, action taken, date of onset and recovery, maximum intensity and outcome. The subjects will be asked to assess the intensity of the reported Adverse Event according to the following scale:

Mild = awareness of sign or symptom, but easily tolerated
Moderate = discomfort sufficient to cause interference with normal activities
Severe = incapacitating, with inability to perform normal activities.

A Serious Adverse Event is an adverse event occurring during any phase of the study and at any dose of the investigational product or placebo, which fulfils one or more of the following criteria:

- Results in death;
- Is immediately life-threatening;
- Requires in-subject hospitalization;
- Results in persistent or significant disability or incapacity.

The causality of Serious Adverse Events (i.e. the relationship to study treatment) will be assessed by the investigators, who in completing the relevant Case Report Form must answer ‘yes’ or ‘no’ to the question “Do you consider that there is a reasonable possibility that the event may have been caused by the study medication?” The following factors should be considered when deciding if there is a “reasonable possibility” that an Adverse Event may have been caused by the investigational product.

- Time course of events and exposure to suspect drug – did the AE occur in a reasonable temporal relationship to the administration of suspect drug?
- Dechallenge experience – did the AE resolve or improve on stopping or reducing the dose of the suspect drug?
- Rechallenge experience - did the AE reoccur if the suspected drug was reintroduced after having stopped?
- Laboratory tests – has a specific laboratory investigation confirm the relationship?
- No alternative cause - the AE cannot be reasonably explained by another aetiology such as an underlying disease (not previously present), other drugs or environmental factors.

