4.4 Measurements recorded daily in a diary

A diary will be filled in at home during the entire study in the morning after taking the morning dose and at night after the evening before going to bed. The following variables will be recorded:

- i) Intake of study medication (if, time and if with food)
- ii) Occurrence of any adverse effects.
- iii) Intake of any incidental medication

The subjects will record the time (morning and evening) that the study medication has been taken. The recordings are a measurement of compliance.

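### The synopsis singles out agitation by how often and how strongly it occurs, but the diary, adverse event form and analysis are not built to measure this, so frequency can be recovered only crudely

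*Combined protocol and SAP*

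**What the plan says.** **Endpoint.** The synopsis (Endpoints, Safety) opens with "Adverse events, especially frequency and intensity of agitation episodes", followed by vital signs and laboratory tests. The body does not carry agitation forward. Section 4 defines safety as "type, severity, duration, treatment and amelioration of each of the adverse effects occurring during respective treatments", and section 4.1 lists adverse events by type and frequency; neither names agitation.

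**Capture.** The diary in section 4.4 has three items: intake of study medication, "Occurrence of any adverse effects", and incidental medication. It is kept at home throughout the study, once at night and once "in the morning after taking the morning dose". At visits, a standard question is asked: "Have you had any health problems since the previous visit". Events go onto a form with onset and recovery dates, outcome and maximum intensity, graded mild, moderate or severe (section 4.4.1). Adverse events are drawn from both the interview and the diary.

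**Children already agitated.** Section 1.2 (Study Rationale, item 4) adds a component of the noninvasive treatment when "restlessness/agitation/anxiety is present significantly in the clinical picture". Section 4.4.1 mentions worsening of an existing condition in its definition of an adverse event, but marks it as having no relevance to this trial.

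**Analysis.** Section 5.2 lists adverse events one by one under each treatment. The synopsis promises summary statistics for safety variables in general. Neither names an agitation rate.

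**The concern.** A frequency of episodes needs a definition of an episode, a count and a known observation time. The plan supplies the observation time but neither of the other two. Recurrent agitation can be entered as a single ongoing event with one grade, so children with very different burdens can look the same on the form. Worsening in a child who was already agitated may not be entered at all, because of the wording of the adverse event definition.

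The secondary objective is to compare the safety profiles of the two treatments. Coarse recording pulls a real difference in episode rates towards no difference, most strongly in the most agitated children. In an open-label trial, a diary prompt tied to dosing can also make parents report more fully under one treatment than under the other.

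**Working it through.** **1. The plan's own figure.** The documents give no number for agitation: no expected rate, difference or precision. The only design figure is the minimum of 25 children (section 5.1, alpha 0.05, power 80%). It cannot be reproduced because no effect size or standard deviation is stated. Solved backwards for a paired two-sided comparison, it implies a standardised difference of (1.96 + 0.84)/√25 = 0.56. The point here does not depend on that value.

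**2. What each instrument retains.**

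| Instrument | Episode count | Intensity |
|---|---|---|
| Diary (4.4) | none; occurrence at each entry | none |
| Adverse event form (4.4.1) | only if each episode is entered separately, which is not required | one maximum per event |
| Visit question (4.4.1) | recall over 8 weeks between V1, V2, V3 and V4, then 52 − 24 = 28 weeks to V5 | via the form |
| Analysis (5.2) | no rate defined | listing only |

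Example: over 56 days, one episode a week is 8 episodes and five a day is 5 × 56 = 280. Both can appear on the form as one ongoing event.

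**3. What occurrence-only entries lose.** Two entries a day over 8 weeks give 2 × 56 = 112 half-days per child per period. The rates below are assumptions, since the documents give none. I also assume that episodes follow a Poisson process spread evenly over the two half-days, that every entry is completed, and that the parent names the event as agitation. With λ episodes a day, the chance that a half-day is marked is q(λ) = 1 − exp(−λ/2), and the expected number of marked half-days is 112 × q(λ).

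| True rate per day | Marked half-days of 112 | Apparent ratio (true ratio 2) |
|---|---|---|
| 0.1 to 0.2 | 5.5 to 10.7 | 1.95 |
| 0.5 to 1 | 24.8 to 44.1 | 1.78 |
| 1 to 2 | 44.1 to 70.8 | 1.61 |
| 2 to 4 | 70.8 to 96.8 | 1.37 |
| 4 to 8 | 96.8 to 109.9 | 1.14 |

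The loss is slight when episodes are rare and severe when there are several a day.

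**4. Prompting under each treatment.** The noninvasive treatment is given for 6 of 8 weeks (sections 3.1.1 and 3.3.1), so a morning dose can exist on at most 6 × 7 = 42 of 56 days. This is an upper bound: several components are prescribed per day with no time of day stated (section 1.2). Cord blood is a single infusion, so when it comes first there is no daily dose on any of the 56 days that follow.

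**5. What a count field would provide.** 25 children × 56 days × 2 periods = 2,800 child-days, or 1,400 per treatment.

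**6. Is a pre-treatment count needed?** For one child with a shared baseline, (A − baseline) − (B − baseline) = A − B. The baseline cancels from the treatment contrast. It helps only to describe agitation at entry and to show worsening under both treatments.

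**The case against.** The strongest reply is that the plan already has a workable system: a twice-daily diary, a form with dates and a three-grade scale, and two sources of reports. Much of this stands, and it rules out several stronger readings.

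- A reader might infer that agitation is the main safety endpoint. It is stressed within the first of three synopsis items, and section 4.1, which carries the heading for primary safety endpoints, does not name it.
- A reader might infer that frequency cannot be measured. Marked half-days and dated events do allow a crude frequency, and a fairly good one when episodes are rare. Intensity is graded, though only at its maximum per event.
- A reader might infer that the data collapse to one yes or no per child and treatment. Nothing in section 5.2 does this; events are listed individually.
- A reader might infer that the missing baseline undermines the comparison. The synopsis asks for change only in vital signs and laboratory tests, and the baseline cancels from the within-child contrast.
- A reader might take 42 against 0 days as the actual gap in capture. The 42 is a ceiling. The night entry does not depend on a dose, and the diary runs throughout the study, so unequal capture is a risk and not a documented fact.

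The diary form itself is not in the documents and may be richer than its summary. Even so, the reply does not supply an episode definition, a count or an agitation analysis, and section 4.4 describes the content of the diary as occurrence only.

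**Conclusion.** The concern holds as a mismatch between a stressed endpoint and the means of measuring it. Followed as written, the plan yields a crude frequency and one maximum grade per reported event. In the illustration, a true doubling appears as anything from 1.95 down to 1.14, depending on how common episodes are. Those ratios rest on the assumed rates, complete entries and the Poisson model; incomplete or unnamed entries would add further loss.

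Two features add to the problem. The adverse event definition may leave out worsening in children whom section 1.2 expects to be agitated at entry. The dose-linked morning entry may also make reporting uneven between treatments; the documents do not allow the size of that effect to be estimated. The plan should be changed before data are collected, because missing counts cannot be rebuilt afterwards. This is a limit on one safety measure and does not invalidate adverse event reporting as a whole.

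**What to change.** - **Section 4.4:** add two parent-completed fields, the number of agitation episodes that day and the worst intensity on the existing three-grade scale, with a one-line definition of an episode. Set the entries at fixed times whether or not medication is taken.
- **Section 5.2:** define episodes per week as 7 × episodes ÷ days with a completed entry. Compare it within child between the two 8-week periods (weeks 0–8 and 8–16), and summarise worst daily intensity in the same way. Any carry-over between periods affects this comparison as it does the others; a better diary does not remove it.
- **Sections 1.2 and 4.4.1:** reconcile the expectation of agitation at entry with the treatment of worsening in the adverse event definition. The count field would record such worsening in either case.
- **Optional:** start the diary at V0, to describe pre-treatment agitation and detect worsening under both treatments. The V0–V1 interval must be reconciled first: section 3.1.1 gives 7–14 days and section 3.3.1 gives 14–21. At two entries a day, these give 14–28 or 28–42 entries.

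The cost is two more fields in a diary that parents already keep, a small extra daily burden, and a short addition to section 5.2. No visit is added and no treatment changes.
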